### 10.2 Randomization *Not applicable*

### 10.3 Blinding *Not applicable.*

### 10.4 Planned Interim Analyses *(if applicable)*

Not applicable

### 10.5 Safety Review *(if applicable)*

## 10.6 Final Analysis Plan

**Primary Objective:** To estimate mean, variance, and quantiles in IP measured by urinary Lacutlose/Rhamnose ratio in in neonates born between 24 and 32 weeks of gestational age.

Sample quantiles of the distribution of IP (as measured by urine LA/Rh ratio) will be calculated at each time point. In addition, we will use mixed effects models to estimate the mean and variance of urine La/Rh. By including other terms in the model we will be able to assess whether high IP (La/Rh ratio  $>0.05$ ) is affected by gestational age, birthweight, sex or *feeding type (mother's own breast milk only, donor breastmilk, preterm formula only, or both breast milk and preterm formula).*

**Secondary Objective:** To evaluate the performance of stool calprotectin, sIgA, and lactoferrin as markers for intestinal permeability *in vivo* as established by the gold standard urine La/Rh in preterm neonates.

**Assessing the relationships between stool markers and urine La/Rh ratio:** To quantify the association between stool calprotectin, sIgA, and lactoferrin, and urine La/Rh ratio, we will calculate Pearson Correlation Coefficients. If the distribution of either variable exhibits substantial skewness we will substitute Spearman Correlation Coefficients. In addition, we will perform sub-group analyses by gestational age or birthweight.

**Assessing the sensitivity and specificity of calprotectin, sIgA, and lactoferrin for identifying children with leaky gut syndrome using an ROC analysis.** Leaky gut syndrome will be defined as having a urinary La/Rh ratio of greater than 0.05 at 7-10 d (12). Using this definition, we will assess the sensitivity, specificity, and predictive value of calprotectin, sIgA, and lactoferrin on each day for identifying those with leaky gut syndrome. An analogous calculation will be made to estimate specificity. We will perform these calculations for a large range of cut-offs for the stool markers, and summarize the findings using an ROC curve. The area under the ROC curve (AUC) will be calculated using an empirical approach to provide an overall summary measure of the performance of **calprotectin, sIgA, and lactoferrin** as measures for leaky gut syndrome.

**Handling missing data or dropouts.** Our analysis of the correlation between calprotectin, sIgA, and lactoferrin and IP will be based on an “available data” approach. That is, if a child missing data due to lack of stool sample or sufficient urine collection, information from that time point will not be included in the analysis. We think this is reasonable because in that situation both and IP will be unknown and imputing both would result in very limited additional information. For the analysis of the degree to which calprotectin, sIgA, and lactoferrin can predict leaky gut syndrome, we will initially do an analysis based on the available data, but in a secondary sensitivity analysis we will see how our estimates are affected if we assume that all those children who dropped out due to illness or deteriorating condition actually developed leaky gut syndrome.

**Stool bacterial community characterization:** DNA will be extracted using the protocols developed and validated at IGS that routinely obtain between 5 and 10 µg of high-quality whole genomic DNA. 16S rRNA gene amplicon sequencing will be performed on Illumina MiSeq platform, using standard methods developed for the NIH Human Microbiome Project and by our group at IGS. Bioinformatics analyses will be performed to calculate bacterial types and their relative abundance. A TaqMan® PanBacterial quantitative PCR assay targeting the 16S rRNA gene, designed and validated by our group at IGS, will be used to estimate the true bacterial abundance per gram of stool. Together the relative proportion and absolute copy number of each individual bacterium will be calculated. Metabolome profiling will be performed using LC/MS (Liquid chromatography/mass spectrometry) by Metabolon, Inc. from 1:2 fecal to PBS solution according the company’s sample preparation protocol. Fecal calprotectin biochemical test (CALPR) will be used as an indicator for pathological inflammation of the bowel wall.

**Discriminatory classifier computation:** Three major procedures are involved to build a discriminatory classifier using supervised machine classifiers to identify high or low intestinal permeability. (1) Data collection. Upon the recruitment of preterm infants at <5d of age and

gestational age (GA) at 24-32 weeks, information including extensive data on demographics, obstetric and neonatal factors, medication exposures, and feeding practices will be obtained. Fecal specimen will be collected to generate bacterial community composition and structure using high-throughput sequencing of 16S rRNA gene amplicon and to calculate bacterial total copy number using quantitative PCR. Urine specimen will be used to measure the non-metabolized sugar lactulose (La) and rhmnose (Rh) concentration using high-pressure liquid chromatography (HPLC), and their ratio will be used to calculate high IP ( $La/Rh > 0.05$ ) and low IP ( $La/Rh \leq 0.05$ ). (2) Discriminatory classifier generation. The bacterial abundance and neonatal information will be used to form the data matrix and the high or low IP category will be used to “label” a sample as its class, which is used in supervised machine learning scheme with cross-validation (construct model on a sample set and evaluate on a different sample set to avoid over-prediction) to direct generating the classifier after data preprocessing and evaluation. The most discriminatory features (i.e. bacterial species and/or neonatal factors) will be characterized by its contribution to identify a sample in a high or low IP class. (3) We will evaluate the contribution of each discriminatory feature to IP classification using permutation importance measurement (5).

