*Measurement of Intestinal Permeability:* The measurement of the urinary excretion of orally administered isotonic solution of non-metabolized sugar probes have been used extensively for 30 years to assess intestinal permeability in health and disease in adults (3-9) and in preterm (10-13) and term infants (13-15) as well as older children. Lactulose, a disaccharide is a constituent of infant formulas (10) and is safe treatment for constipation (16) at doses 8-15 times higher than used in the assessment of intestinal permeability. L-Rhamnose is a naturally occurring monosaccharide without known biologic effects. It is found in the polysaccharides of gums, cardiac glycosides, and foods such as oranges, French beans, winter cabbage, and carrots (17) and is used in food flavoring (10). It is not absorbed by the human small intestine and reaches the colon where fermentation may produce propionate. The percent urinary excretion of orally administered lactulose and rhamnose are markers of the intestinal paracellular and transcellular pathways, respectively. The sugar probe tests have been used to safely estimate intestinal permeability in pediatric conditions including celiac disease (18), atopic eczema (19, 20), cystic fibrosis (21, 22), major burns (23) and diarrhea (24-26). The sugar probe has also been safely used to assess intestinal permeability in ill newborns with birth asphyxia (10), necrotizing enterocolitis (NEC) (11) and congenital heart disease (15, 27). A recent review confirmed that the use of the sugar absorption tests have been found to be safe in newborns (28). We have summarized the literature of the use of lactulose and L-rhamnose as sugar probes in studies of preterm and term infants (Table 1) and older infants and children (Table 2) (see IND section 6.2).

*Intestinal functions and prematurity:* Epithelial barrier integrity is itself dynamic and matures over time starting soon after birth, though the mechanisms regulating dynamic permeability are poorly understood. Low birth weight, prematurity, and early postnatal age are associated with a leaky gut (34). Although intestinal permeability (IP) is higher at birth in preterms than term infants, there is usually rapid maturation of the intestinal barrier over the first few days of life in both populations (34). Diet also affects intestinal permeability with breast milk feeding lowering

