### 2.3 Preliminary Data

[figure not shown]

**Figure 1.** Microbial community diversity and intestinal permeability at study time points day 1, 8, and 15 for a cohort of 43 preterm infants (<33 weeks gestational age). Microbial community diversity is calculated as OTU richness based on 16S rRNA gene amplicon high-throughput sequencing. Intestinal permeability was calculated as the ratio of non-metabolized sugar probes

gestational age (<31.7wk) were identified to be the most discriminatory features for elevated IP by supervised learning scheme, reaching an accuracy of 86.1%. (5) *Clostridiales* and *Bifidobacteriales* are the most abundant bacteria groups in later stages (phase II/III at 6-18

Our analysis of the initial cohort of 43 preterm infants recruited for the IND protocol, and others' previous studies have shown that IP is high at birth in preterms (<33wk gestation) with a rapid maturation of the intestinal barrier over the first 2 weeks. However, in some infants, high IP persisted and/or recurred in association with altered levels of the normal microbiota (bacteria community composition). Specifically, we observed that (1) rapid maturation of intestinal barrier function, characterized by decreased IP, correlates with increased microbial community diversity (Figure 1), and most outstandingly, the increased abundance of beneficial bacteria *Clostridiales* (Figure 2); (2) *Clostridiales* is highly transcriptionally active and co-active with the probiotic bacterium *Bifidobacterium*; (3) neonatal factors, including early introduction of breast milk, shorter period of antibiotic exposure, and later gestational age, favor the early colonization of the gut microbiota by members of *Clostridiales* and *Bifidobacterium*, which altogether are associated with improved intestinal barrier in preterm infants; (4) low *Clostridiales* spp. abundance (<5%) and early

months of age) as shown in Figure 2, suggesting a process of gaining prosperity of these two bacterial groups during intestine development after birth. Altogether our preliminary results suggest the early colonization of the natural occurring probiotics strains *Clostridiales* and *Bifidobacterium* strongly associate with rapid maturation of intestinal barrier function, and their measurement are highly promising for early detection and as potential nutritional supplement to prevent NEC in the high-risk preterm population.

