We propose in this study to recruit additional 157 preterm subjects and to combine with our existing 43 preterm subjects to form a statistically powered cohort at 200 (justified in study size analysis in research design), to address our hypothesis that the two naturally occurring beneficial bacteria *Clostridiales* and *Bifidobacterium* are rapidly gaining prosperity during normal intestine development in association with improved barrier function measured by La/Rh ratio. Overall, this continuation of the initial study builds on the previous findings that identified commensal bacteria *Clostridiales* and *Bifidobacterium* species as a strong indicator to the lowered IP and rapid maturation of intestinal barrier, to substantiate measurement of these probiotic strains combined with associated neonatal factors to form an accurate, rapid detection of intestinal permeability abnormality.

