#### **6.9 Product Administration (include allowable time windows)**

Each enrolled preterm neonates will be administered a 1 mL/kg La/Rh solution (8.6 g of lactulose + 140 mg of rhamnose/100 mL) via a clinically indicated OG or NG tube once between 7-10 d of age. The La/Rh solution will be administered by gavage with an enteral feed. Total volume of La/Rh ingested will be recorded. Urine will be collected for a 4-hour period *with cotton balls*. Total volume of urine during the 4 hour collection will be recorded. The urine will be aliquoted and 4 ml of urine saved for analysis. Nursing staff in the NICU will be trained in the procedures prior to study initiation. Only trained NICU staff will be allowed to be responsible for administering the La/Rh solution and collecting the urine. A minimum of 2 ml of urine will be collected. If urine leaks around the cotton balls, then the diaper will be weighed and the diaper weight will be used to estimate the urine volume for the 4 hour collection period. If less than 2 ml urine is collected, then the test will be repeated on another day within the 7-10d window by

administering 1 ml/kg La/Rh solution (8.6g of lactulose + 140 mg of rhamnose/100mL) via an OG/NG tube followed by a 4 hour urine collection. The urine will be stored at -80°C until processed. The sugars will then be measured in urine by HPLC.

Urine La and Rh will be measured in the lab of our collaborator [name] from the University of Calgary, Canada.

*Stool calprotectin, sIgA, and lactoferrin will be measured by commercial ELISA kits.*

Rescue Therapy- NA

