### **7.6 Halting Criteria/Rules**

#### **7.6.1 Stopping Rules for Individual Subjects**

A pre-dose checklist for evidence of feeding intolerance will be completed prior to La/Rh administration. The Lactulose/Rhamnose administration will be re-scheduled within the study window if the clinically indicated gastric residual is obtained and measures >50% of the previous nutritive feeding volume, and/or contains bile or gross blood, or is hemoccult-positive. If these GI signs are present throughout the study window, the La/Rh test will not be administered. Other conditions that would result in delay or discontinuation of the La/Rh test include hypotension requiring pharmacologic support, clinical or radiographic signs of intestinal ileus or NEC. The subject will continued to be followed until postnatal day 21±2 d or discharge/transfer which ever occurs first.

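### The covariate model for intestinal permeability names neither postnatal age at the La/Rh test nor cohort, and no rule says which first-cohort values count as days 7-10

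*Combined protocol and SAP*

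**What the plan says.** Section 2.5 sets the primary objective: the mean, variance and quantiles of the La/Rh ratio at 7-10 days of life. For the analysis, section 10.6 states that "we will use mixed effects models to estimate the mean and variance of urine La/Rh". It then adds other terms to assess whether high IP "is affected by gestational age, birthweight, sex or" feeding type. The fixed and random effects of the base model are not listed.

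Four other parts of the protocol bear on this:

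- **Maturation.** Section 2.1 says that "there is usually rapid maturation of the intestinal barrier over the first few days of life in both populations", meaning term and preterm infants. Section 2.3 describes IP as high at birth in preterm infants, "with a rapid maturation of the intestinal barrier over the first 2 weeks".
- **Test day.** Section 6.9 gives the solution "via a clinically indicated OG or NG tube once between 7-10 d of age" and repeats the test on another day in the window if less than 2 ml of urine is collected.
- **Postponement.** Section 7.6.1 says: "The Lactulose/Rhamnose administration will be re-scheduled within the study window", when the gastric residual is large or contains bile or blood. Hypotension on drug treatment and signs of ileus or NEC also delay or cancel the test.
- **Pooling.** Section 2.3 plans to recruit 157 more infants and "combine with our existing 43 preterm subjects to form a statistically powered cohort at 200". Those 43 were measured on study days 1, 8 and 15. The revision history treats study day 8 as only roughly equal to ages 7 to 10 days.

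**The concern.** Age at the test can vary by three days among the new infants, in a period when the protocol expects IP to be changing. The day is not assigned at random. The postponement rules depend on clinical condition, which plausibly follows gestational age, birthweight and feeding, the factors whose effects are to be assessed. A difference between groups could then partly reflect when the infants were tested.

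Cohort raises a similar problem. About a fifth of the data come from an earlier period with a different timing rule, and the plan does not say which of those values belong to the 7-10 day estimate.

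The stool analyses are exposed as well. Section 2.3 links falling IP with rising microbial diversity as infants mature, so postnatal age may drive both sides of the association that the sample size of 200 was meant to support.

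**Working it through.** The plan states no figure on this point, so there is none to reproduce. The check compares the model terms with the timing rules and then shows what could be at stake under stated assumptions.

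**1. Terms named.** Section 10.6 lists gestational age, birthweight, sex and feeding type. Age at the test and cohort appear nowhere in section 10 as model terms. Age at the test can be derived from the birth and dosing dates.

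**2. Share on the study-day clock.** 43 / 200 = 21.5%.

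**3. Age of the first cohort at study day 8.** Assumption: it enrolled under the current rules, at under 5 days of age (section 4.1) and starting within 24 hours (section 6.2). Study day 1 then falls at age 0-5 days. Study day 8 is seven days later, at age 7-12 days. Days 11 and 12 lie outside the window.

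**4. Illustration of the age effect.** The documents give neither a daily rate of change nor the spread of La/Rh. Assume a fall of f = 5%, 10% or 20% per day.

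- Moving a test from day 7 to day 10 multiplies La/Rh by (1 - f)^3 = 0.86, 0.73 or 0.51.
- If one group is tested on average one day later than another, its unadjusted geometric mean is multiplied by (1 - f) = 0.95, 0.90 or 0.80.
- For the binary outcome, take the 83% with high IP in the first cohort as the reference and assume a log-normal ratio with log SD s. Three days later the share is Φ(Φ⁻¹(0.83) + 3 ln(1 - f) / s).

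| Log SD | f = 5% | f = 10% | f = 20% |
|---|---|---|---|
| 0.8 | 0.78 | 0.71 | 0.55 |
| 1.0 | 0.79 | 0.74 | 0.61 |
| 1.2 | 0.80 | 0.76 | 0.65 |

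These values show only how sensitive the result is if IP falls steadily. They do not estimate the bias in this study.

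**5. Room in the model.** At 83% high IP, 200 × 0.17 = 34 infants have low IP. The named covariates use 1 + 1 + 1 + 3 = 6 degrees of freedom, with gestational age and birthweight linear and four feeding types. Adding age and cohort makes 8. For a binary model, low-IP infants per degree of freedom go from 34 / 6 = 5.7 to 34 / 8 = 4.25.

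**The case against.** The primary objective is descriptive. Its window is part of what is being estimated, so quantiles over days 7-10 need no age adjustment. This stands, and it limits the point to the covariate assessment, the pooling and the stool analyses. The descriptive estimates still need a rule for values that may lie outside the window.

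The base model is also unlisted. Section 10.6 speaks of several time points, so a visit or time term may be intended. The omission is thus a lack of specification and not an explicit exclusion. Even so, a study-day term would not be postnatal age, and nothing suggests a cohort term.

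A reader might infer that sicker infants are tested later, after IP has fallen, so that the gestational age effect is pulled towards zero. The documents do not establish this. Section 2.3 says that high IP continued or returned in some infants, and postponed infants may be among them. Under section 7.6.1, infants whose signs last through the window are never tested. Section 6.9 postpones for low urine volume, which is a different reason.

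A reader might also infer that the cohorts differ by site. The second site was dropped only in the 2019 revision, after the 2018 revision had moved to a single test, and the documents do not say how many infants in either cohort came from it.

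Finally, adjustment is not neutral. If illness both delays the test and raises IP, age at the test partly stands in for illness, and conditioning on it may remove part of a real effect. This stands, and it is why results with and without the age term are needed.

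**Conclusion.** The point holds for the covariate model and the pooling. Given the protocol's own account of rapid maturation, clinically driven test days and two timing rules, effects estimated without age at test and cohort may be confounded by both. The size and direction cannot be derived; the figures in the illustration rest on an assumed daily fall and an assumed spread, and the short window limits the effect among the new infants.

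That some first-cohort tests fell outside days 7-10 is possible but not shown. It depends on applying the current enrolment rule to infants who may have entered under different wording. The secure part is that 21.5% of the planned sample was timed differently and that the plan has no rule for admitting those values. The change is worth making before analysis, because a later choice could be driven by the data.

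**What to change.** 1. **Primary estimates.** Include a first-cohort value in the 7-10 day mean, variance and quantiles only if the actual age at the test was postnatal day 7-10. Report these estimates with and without the first cohort.
2. **Covariate model.** Add exact postnatal age at dosing and a cohort indicator. Preferably model continuous log La/Rh, because about 34 low-IP infants are few for a binary model with 8 degrees of freedom. Show the gestational age, birthweight and feeding effects with and without the age term, since test day may partly reflect illness.
3. **Stool analyses.** The planned correlations have no place for fixed terms, so add partial Pearson or Spearman correlations adjusted for postnatal age and cohort. Offer both variables as candidate features in the classifier.

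The cost is two degrees of freedom, a little more analysis, and possibly a few first-cohort values leaving the primary estimate. No new procedure is needed. Adjustment for age will not recover infants who were never tested; that is a separate missing-data question.

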**Endpoints:**

Onetime measurement of *in vivo* permeability determined by the urine La/Rh ratio between 7-10 days of age and serial stool microbiome changes between postnatal d5-d14 and at PND21 in a cohort of preterm neonates. The goal is to determine the changes in the intestinal microbiome characteristics in association with impaired intestinal barrier function (La/Rh  $\geq 0.05$ ) at 7-10 days in preterm neonates.

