**Secondary Objectives:**

- 1) To assess stool microbiome characteristics in association with intestinal permeability in preterm infants measured by the urinary lactulose/rhamnose ratio

- 2) *To analyze the correlation of stool calprotectin, sIgA, and lactoferrin to urinary lactulose/rhamnose ratio and stool microbiome characteristics in neonates born between 24 and 32 weeks of gestational age.*

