#### Postnatal d7-10

- ∞ In vivo IP will be determined by means of the urine La/Rh test. Briefly, preterm neonates will be administered a 1 mL/kg La/Rh solution (8.6 g of lactulose + 140 mg of rhamnose/100 mL) via a clinically indicated OG or NG tube. The La/Rh solution will be prepared by the Investigational Drug Pharmacy (IDS) and administered by gavage. Starting at the time of the dose of the La/Rh solution, urine will be collected for a 4-hour period with cotton balls. If a participant does not require an OG/NG tube the solution will be administered orally by nippling.
- ∞ Continue collecting available stool samples daily until PND14 and single sample on PND21 for microbiome, calprotectin, sIgA, and lactoferrin analysis. Record daily weight, and weekly height, and head circumference.

- ∞ Demographic and clinical data will be collected from the chart.
- ∞ Collect adverse events from medical chart.

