#### **6.8 Final Study Visit (include allowable time window)**

##### **PND21 (± 2d) or discharge/transfer whichever comes first**

- ∞ *Final collection of stool samples for analysis*
- ∞ Medication history including the number of packed red blood cell transfusions and total volume received will be collected from the chart
- ∞ *Record daily weight, and weekly height, and head circumference.*
- ∞ Collection of adverse events from medical chart.

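### Section 10.6 specifies no analysis that estimates the serial stool microbiome endpoint or tests the Clostridiales and Bifidobacterium hypothesis, and none for the marker-microbiome half of Secondary Objective 2

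*Combined protocol and SAP*

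**What the plan says.** The Endpoints entry of the protocol summary lists, beside the single La/Rh measurement, "serial stool microbiome changes between postnatal d5-d14 and at PND21 in a cohort of preterm neonates". It then states the purpose: "The goal is to determine the changes in the intestinal microbiome characteristics in association with impaired intestinal barrier function" at 7-10 days. Section 2.3 gives the hypothesis that Clostridiales and Bifidobacterium "are rapidly gaining prosperity during normal intestine development in association with improved barrier function measured by La/Rh ratio".

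Under Secondary Objectives, the first is worded more generally: "To assess stool microbiome characteristics in association with intestinal permeability in preterm infants". The second asks how stool calprotectin, sIgA and lactoferrin correlate with "urinary lactulose/rhamnose ratio and stool microbiome characteristics in neonates born between 24 and 32 weeks of gestational age".

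Section 6.4 sets the stool schedule: "Continue collecting available stool samples daily until PND14 and single sample on PND21". Section 6.8 places the final visit at "PND21 (± 2d) or discharge/transfer whichever comes first".

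The microbiome part of section 10.6 consists of laboratory and bioinformatic quantification, then a supervised classifier. The inputs are described in these words: "The bacterial abundance and neonatal information will be used to form the data matrix and the high or low IP category will be used". Each sample thus carries its infant's IP category as its class. Features are then ranked by permutation importance.

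**The concern.** The endpoint is about change over time and the hypothesis is about two named taxa increasing. An analysis that answers either needs abundance as an outcome, age as a predictor, a term linking the age trend to IP, and allowance for repeated stools from the same infant. None of these is specified for the microbiome data.

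Followed as written, the plan would end with a ranked list of features and a classification accuracy. It would give no rate of increase, no interval and no test for either taxon. If the model is chosen only after the data are seen, then taxon, time window and IP cut-off are also chosen then, and a result for the stated hypothesis would be hard to defend as pre-specified. The plan also does not say which stool or day enters the classifier, or whether cross-validation keeps one infant's stools together.

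**Working it through.** **1. What section 10.6 offers, item by item**

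- Sample quantiles and a mixed model: the outcome is urine La/Rh, measured once in each new infant (section 6.9).
- Pearson or Spearman correlations and ROC curves: calprotectin, sIgA and lactoferrin against La/Rh only.
- Stool bacterial community characterization: relative proportion and absolute copy number per bacterium, with no inference.
- Classifier: abundance and neonatal information predict the high or low IP label. Postnatal age at stool is not listed as a feature.
- Stool markers against microbiome features: nothing.

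**2. The plan's own sample size figure**

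Section 10.5 gives 166-236 for the microbiome analysis. The precision formula for a sensitivity is N = 1.96² x Se(1 - Se) / (0.05² x 0.83).

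- Se 0.90: 3.8416 x 0.09 / 0.002075 = 166.6
- Se 0.85: 3.8416 x 0.1275 / 0.002075 = 236.0

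So the range matches cross-sectional precision at Se 0.85-0.90. The stated lower bound of 0.80 would give 296.2, which is a separate matter. No longitudinal quantity enters the figure.

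**3. What a time-blind, sample-level classifier recovers**

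The documents give no variances. Assume one taxon, between-infant and residual SD of 0.7 log10 each, daily stools on days 5-14, and 166 high-IP against 34 low-IP infants (83% and 17% of 200). The SD of a difference between two samples from different infants is sqrt(2 x (0.49 + 0.49)) = 1.4.

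- Constant shift of 0.5, both groups flat: AUC = Φ(0.5/1.4) = 0.64. If both rise 0.1 per day, simulation gives 0.634. The AUC hardly moves, although growth went from none to 0.1 per day.
- Equal overall means, low-IP infants rising 0.1 per day, high-IP flat: AUC = 0.50. A comparison of per-infant slopes found the difference in essentially all of 500 simulated runs.
- Both groups level at day 5, then low-IP infants rising 0.1 per day: AUC is the mean of Φ(0.1k/1.4) for k = 0 to 9, which is 0.62. There is signal here, but still no slope.

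**4. Amount of data**

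Days 5-14 plus day 21 give up to 11 stool-days per infant. Section 2.3 says 157 of the 200 infants are new: 157 x 11 = 1,727 at most. The earlier 43 were reported at study days 1, 8 and 15.

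**5. Illustrative detectable difference in growth**

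Assume 70% of day 5-14 stools available, slope SD 0.05-0.10 log10/day and independent residuals. The sum of squares of days 5-14 is 82.5, and x 0.7 = 57.75.

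- Slope variance: 0.05² + 0.49/57.75 = 0.01098, or 0.10² + 0.49/57.75 = 0.01848.
- sqrt(1/166 + 1/34) = 0.188, so the SE of the slope difference is 0.0197 or 0.0256 log10/day.
- Alpha 0.05, 80% power: x 2.80 x 9 days = 0.50-0.64 log10.
- Alpha 0.025 (first Holm step for two taxa): x (2.24 + 0.84) x 9 = 0.55-0.71 log10.
- Alpha 0.05 with residual SD 0.35 (slope SD 0.05) to 1.4 (slope SD 0.10): 0.32-0.99 log10.
- Alpha 0.05, residual SD 0.7, new infants only (about 130 against 27): 0.56-0.72 log10.

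**The case against.** The formal objectives do not ask for growth rates. The primary concerns the La/Rh distribution, and the first secondary asks only for association. Section 2.3 follows the hypothesis with a detection aim, which a classifier with permutation importance serves well. The revision history says stools were concentrated around the IP test to study correlation of composition with IP. On this view the classifier is the intended analysis and the summary is loosely worded.

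Part of this stands. The classifier is appropriate for detection and should stay. But the Endpoints entry refers to serial changes and makes determining those changes the goal, and section 2.3 names two taxa and a direction. Detection does not deliver either.

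Three stronger readings are tempting, and the documents do not support them:

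- A reader might infer that the classifier is incapable of showing change. Postnatal age is neither listed nor excluded as a feature, so the supportable statement is that the method as specified does not show change. The AUC of 0.50 in the working also depends on trajectories that cross; with a common start it is 0.62.
- A reader might multiply 11 stool-days by 200 infants. That applies the current schedule to 43 infants who were on a different one.
- A reader might count the microbiota-IP correlations in section 10.5 as a planned analysis. They appear only as sample size rationale, and section 10.6 has no matching method.

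**Conclusion.** The point holds as a gap in specification. A declared endpoint, a stated hypothesis and half of a secondary objective have no analysis that would estimate or test them. It should be closed before the microbiome data are analysed. The primary objective does not depend on it.

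That conclusion rests on the text alone. The detectable differences are illustrative only: about 0.55-0.71 log10 over 9 days at alpha 0.025, and 0.32-0.99 at alpha 0.05 across the wider range of residual SD. They rest on assumed variances and stool availability. They use two IP groups, whereas the model proposed here uses continuous log La/Rh, and they ignore covariate terms. They also assume La/Rh is available in all 200 infants, although section 7.6.1 allows the test not to be given.

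With one La/Rh value per new infant, improvement in barrier function within an infant cannot be modelled for them. What can be estimated is the taxon trajectory in relation to IP at 7-10 days.

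**What to change.** Keep the classifier for the detection aim and add the following to section 10.6.

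- **Hypothesis model.** For Clostridiales and for Bifidobacterium, fit a linear mixed model of log10 absolute abundance, which the plan already derives. State beforehand the rule for zeros or non-detects. Terms: actual postnatal age at stool, log La/Rh at 7-10 days and their interaction; gestational age, feeding and antibiotic exposure, each with its interaction with age; random intercept and slope per infant. The covariate-by-age terms are needed because section 2.3 links these factors to both colonization and barrier function. Actual age matters because the last stool may be taken at discharge or transfer.
- **Result to report.** The age-by-log La/Rh interaction with 95% CI, with tests Holm-adjusted over the two taxa.
- **Earlier cohort.** State how the 43 infants on a different schedule enter the model.
- **Secondary Objective 2.** Analyse calprotectin, sIgA and lactoferrin against microbiome features separately, allowing for repeated stools within infant. Do not enter the markers as covariates in the hypothesis model: they are plausibly downstream of barrier function and would change what the interaction means.

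The cost is SAP wording and a small amount of extra analysis on data already collected. The downside is more model terms with only about 34 low-IP infants, so intervals may be wide.
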